9.1.3. Collection of Specimens

After consenting patients, peripheral blood samples will be collected at baseline before initiation of treatment and at the time of any change in response status as assessed on follow-up imaging studies. All attempts will be made to draw the blood with currently scheduled venipuncture, but it will also be permissible to draw specifically for this study if necessary.

9.1.4. Handling of Specimens

Approximately 10-16 mL of blood will be obtained from the patient in two 10 ml EDTA (purple top) tube. These tubes of blood will serve as the specimen for both correlative study #1 and #2. In order to facilitate the subsequent analyses all research samples will be collected on Monday-Thursday from 8:00am-3:00pm. Specimens will be put on ice after collection and transported to the Biospecimen Processing Core Laboratory (Room 1826 MBRCC) within 30 minutes of acquisition. All subsamples will be labeled with only the following: patient research ID (obtained from the PI/study coordinator), date/time of collection, type of sample. The labeled sample for correlative study #1 and #2 will then be transported on ice to the laboratory of [name] (HSC 5602) for further processing and analysis.

9.1.5. Analytical Laboratory

The specimens will be processed and analyzed in Health Sciences Center (HSC) laboratory 5602, under the direction of [name]. [name] and his personnel will provide technical support for the isolation of both the serum and cellular component of the samples, and provide overall guidance in experimental design and interpretation of results.

9.1.6. Methods

Need IB buffer (0.5 g BSA in 100 ml MACS buffer, filter). Keep at 4⁰C.

1. Put pad in hood to work on. Mix the tube with blood.
2. Pipet x 250 ul blood in 4 yellow cap BD microtainer tubes (SST – serum separator). Centrifuge Hermle 15000 rpm/4⁰C/5min. While centrifuging, prepare 4 Eppendorf tubes, with label on top – patient ID, initials, and date.
3. Collect the serum in the 4 Eppendorf tubes and freeze at -80⁰C (left freezer, box “[name] Clinical Trials Plasma Samples”).
4. The remaining blood, ~ 8 ml – dilute 1:1 with PBS. Prepare 2 Falcon 15 tubes with 4 ml PBS in each. Divide the blood between the two tubes and add additional PBS depending on the volume of blood. Mix well.
5. Prepare two Falcon 15 tubes with x 4 ml Ficoll. Layer the diluted blood on top of the Ficoll – put the pipettor on “LOW” and “GRAVITY”.
6. Centrifuge at 2000 rpm/25⁰C/20 min with no brake (brake=0, 0). Program Buffy. Go to next step as soon as the centrifuge stops.
7. Collect the plasma from the 2 Falcons in a new Falcon tube. [When incubating at a later step, aliquot the plasma in 10 Eppendorf tubes, labelled with patient ID/initials/date and keep in right

- 80°C freezer, second shelf from bottom, box “Diluted Plasma [name] Clinical Samples”]. Leave ~3-4 mm of plasma on top of the PBMC layer. Next, collect the PBMC layer in a new Falcon tube. Volume is ~4-5ml.
8. Add 5 ml PBS to the PBMCs (10 ml, if some of the Ficoll has been transferred). Mix by inverting 3-4 times. Centrifuge 1500 rpm/5min/4°C (Program No1 Cell spin).
 9. Label 10 Eppendorf tubes 1-10. Take out supernatant and resuspend in 1 ml IB buffer. 10 min ice.
 10. Aliquot the cells in the Eppendorf tubes:
 1. Unstained
 2. 70 ul cells + 5ul CD4 Ab
 3. 70 ul cells + 5ul CD25 Ab
 4. 70 ul cells + 5ul FoxP3 Ab
 5. 70 ul cells + 2ul iNOS Ab
 6. 70 ul cells + 5ul CD80 Ab
 7. 190 ul cells + 5ul CD4 Ab + 5ul CD25 Ab + 5 ul FOXP3 Ab
 8. 190 ul cells + 5ul CD8 Ab
 9. 190 ul cells + 5ul CD80 Ab + 2 ul iNOS Ab
 11. Incubate for 1h at 4°C covered with foil.
 12. Add x 1 ml MACS buffer and centrifuge 1500 rpm 5min/4°C. Repeat.
 13. Resuspend in x 100 ul MACS buffer. Add x 900 ul Methanol (keep at -20°C). Incubate for 30 min on ice, covered with foil.
 14. Centrifuge 2000 rpm/5min/4°C. Resuspend in 1 ml MACS buffer. Centrifuge again.
 15. Samples 1, 2, 3, 4, 7, and 9 – resuspend in x 300 ul MACS buffer, transfer to FACS tubes and keep at 4°C covered with foil. Label the FACS tubes with the name of the antibody.
 16. Samples 5, 6, 8, and 10 – add antibodies for intracellular staining.
 17. Incubate on ice for 1h, covered with foil.
 18. Add x 1 ml MACS buffer to the tubes. Centrifuge 2000 rpm/5min/4°C. Repeat.
 19. Resuspend samples in x 300 ul MACS buffer. Transfer to FACS tubes, keep at 4°C covered with foil.
 20. Bring tubes to the Flow facility.

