9.1.1. Background

Preclinical data suggests that immune checkpoint inhibitors increase the quantity of the activated cytotoxic T-cell subpopulation, with a higher CD8/Treg ratio correlating with more robust immune activation.²⁸⁻²⁹ Additionally, M1/TH1 pro-inflammatory iNOS+/CD80+ macrophages may also be recruited to a tumor and involved in cell-killing in this clinical context.³⁰⁻³¹

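### Section 9.1.6 contradicts itself on which flow-cytometry tubes are stained after permeabilisation; followed literally, it makes the Treg and iNOS+/CD80+ values unreliable

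*Combined protocol and SAP*

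**What the plan says.** All of this is in section 9.1.6 of the combined protocol and SAP (Methods of correlative study #1).

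- Step 9 says "Label 10 Eppendorf tubes 1-10" and resuspends the cells in 1 ml of buffer.
- Step 10 gives contents for tubes 1 to 9 and stops. Tube 4 is "70 ul cells + 5ul FoxP3 Ab" and tube 5 is "70 ul cells + 2ul iNOS Ab". Tube 7, the only one combining the three Treg markers, is "190 ul cells + 5ul CD4 Ab + 5ul CD25 Ab + 5 ul FOXP3 Ab". Tube 9, the only one combining the macrophage markers, is "190 ul cells + 5ul CD80 Ab + 2 ul iNOS Ab". Tubes 6 and 8 hold CD80 alone and CD8 alone.
- Step 13 adds methanol, after the antibodies of step 10 have been incubated and washed off.
- Step 15 says "Samples 1, 2, 3, 4, 7, and 9 – resuspend in x 300 ul MACS buffer, transfer to FACS tubes". These tubes receive no further antibody.
- Step 16 says "Samples 5, 6, 8, and 10 – add antibodies for intracellular staining". It does not say which antibodies.

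The assay serves the correlative objective in sections 1.3 and 9.1, which names four cell populations: CD4+, CD8+, Treg and iNOS+/CD80+. Sections 9.1.2 and 13.3 put the results into univariate and multivariate logistic models of response, and 13.3 plans a nomogram from the multivariate result.

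**The concern.** The tubes that carry FoxP3 or iNOS are not the tubes sent for intracellular staining. If the numbers are followed as printed, the antibodies in the Treg tube and the CD80/iNOS tube meet only cells that have not been permeabilised, while the CD80 and CD8 tubes and a tube with no stated contents go to the intracellular step.

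The Treg level would then be unreliable, and so would the ratio that section 9.1.1 gives as its rationale ("with a higher CD8/Treg ratio correlating with more robust immune activation") and the iNOS+/CD80+ level. The cytometer would still return ordinary-looking numbers, and nothing in sections 9.1.2 or 13.3 would keep them out of the models. Section 9.1.6 stores serum (step 3) and plasma (step 7) but describes no reserve of mononuclear cells from which a mis-stained draw could be repeated.

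**Working it through.** There is no plan figure to reproduce for the tube layout, so the check is a comparison of lists.

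**1. Which tubes hold FoxP3 or iNOS.** The protocol does not say which markers are intracellular. FoxP3 and iNOS are taken to be, as an assumption that step 3 below supports. From step 10, the tubes are 4, 5, 7 and 9.

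**2. Comparison with steps 15 and 16.**

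| Tube | Contents (step 10) | FoxP3 or iNOS? | Sent to |
|---|---|---|---|
| 1 | unstained | no | step 15 |
| 2 | CD4 | no | step 15 |
| 3 | CD25 | no | step 15 |
| 4 | FoxP3 | yes | step 15 |
| 5 | iNOS | yes | step 16 |
| 6 | CD80 | no | step 16 |
| 7 | CD4, CD25, FoxP3 | yes | step 15 |
| 8 | CD8 | no | step 16 |
| 9 | CD80, iNOS | yes | step 15 |
| 10 | not stated | unknown | step 16 |

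The sets {4, 5, 7, 9} and {5, 6, 8, 10} share one member, tube 5. Three of the four FoxP3/iNOS tubes (4, 7, 9) get no antibody after methanol.

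**3. Does one missing line explain it?** Insert one tube at position p in the step 10 list, so that every tube from p onward moves up by one.

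- p = 1, 2, 3 or 4: the FoxP3/iNOS tubes become {5, 6, 8, 10}, exactly the step 16 list.
- p = 5: {4, 6, 8, 10}.
- p = 6 or 7: {4, 5, 8, 10}.
- p = 8 or 9: {4, 5, 7, 10}.
- p = 10: {4, 5, 7, 9}.

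Only an insertion at or before position 4 matches. Step 15 then holds the unstained, CD4, CD25, CD80 and CD8 tubes and the inserted one, none of the listed ones carrying FoxP3 or iNOS. It also brings the count to the ten tubes of step 9.

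**4. Does cell volume rule out a tenth tube?** Tubes 2 to 6 take 5 × 70 = 350 µl and tubes 7 to 9 take 3 × 190 = 570 µl, together 920 µl. The unstained volume is not given; at an assumed 70 µl the total is 990 µl. A tenth tube of 70 µl brings it to 1,060 µl, and one of 190 µl to 1,180 µl, against a nominal 1,000 µl. A line lost at or before position 4 falls among the unstained and single-stain tubes, so 70 µl is the more natural assumption. With two assumed volumes in the sum, the total does not settle whether a tenth tube was intended.

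**5. Does the section 13.2 biomarker power depend on this?** Section 13.2 claims at least 80% power for a 50% difference with CV 0.45, 33 patients, a response rate of 35% and a two-sided 0.05 t-test. Responders: 0.35 × 33 = 11.55, so 11 or 12. The noncentrality is 0.5 / (0.45 × √(1/n₁ + 1/n₂)) on 31 degrees of freedom.

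- 11 v 22: 0.5 / (0.45 × 0.369) = 3.01, power 0.83.
- 12 v 21: 0.5 / (0.45 × 0.362) = 3.07, power 0.84.

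The plan's figure is reproduced. The tube layout does not enter it.

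**The case against.** The strongest reply is that this is a dropped line and not a faulty assay. Steps 9, 15 and 16 agree on ten tubes, only step 10 is one short, and the one-place shift is exact. On that reading steps 15 and 16 send the right tubes to staining after methanol. CD4, CD25, FoxP3, iNOS and CD80 each have a 70 µl single-stain tube and CD8 does not, which suggests what was lost, although that identity is inference. Section 9.1.5 also places the work under a laboratory that guides design and interpretation, and it may well run a correct ten-tube panel.

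Much of this stands, and it rules out several stronger inferences that a reader might draw:

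- That tube 10 does not exist. Step 9 labels it; only its contents are missing.
- That there are no cells left for it. The 1,180 µl total assumes a 190 µl tube.
- That tubes 7 and 9 go unstained. Their antibodies are added, but before permeabilisation.
- That step 16 names only surface-marker tubes. Tube 5 is iNOS.
- That Treg and iNOS+/CD80+ data are lost in every patient at every draw. The documents do not show what was done at the bench.

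The reply does not dispose of the point. Restoring the numbering still leaves step 10 adding FoxP3 and iNOS before methanol with no instruction to hold them back, step 16 naming no antibodies, and one tube undefined. Section 9.1.6 is the only staining method that the protocol gives for these markers.

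**Conclusion.** The concern holds as an internal contradiction among steps 9, 10, 15 and 16, most probably caused by a line lost from step 10 at or before position 4. Read by the step 10 numbering, three of the four tubes carrying FoxP3 or iNOS miss the staining after methanol, among them the only Treg tube and the only combined CD80/iNOS tube. Executed literally, this would make two of the four cell populations in the correlative objective, and the CD8/Treg ratio, unreliable while they still entered the logistic models.

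That consequence rests on two assumptions: that the steps are followed by their printed numbers, and that FoxP3 and iNOS antibodies need permeabilised cells. The second is general assay knowledge, though the protocol's separate intracellular step after methanol is consistent with it. To say that these values cannot be derived at all goes further than the documents allow.

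The ordering fault does not affect the surface staining of CD4, CD25, CD8 and CD80 done at step 10. The primary response endpoint and the section 13.2 biomarker power are also unaffected. The effect is confined to correlative study #1 and the models that use it.

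**What to change.** Reconcile steps 9, 10, 15 and 16 of section 9.1.6:

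- Either restore the missing tube in step 10, or renumber steps 9, 15 and 16 to the nine-tube panel. The laboratory should say which was intended; tube 10 should not be deleted by default, since it may be a control.
- State the contents of every tube.
- Limit step 10 to the surface antibodies (CD4, CD25, CD80, CD8).
- State at step 16 that FoxP3 and iNOS antibodies are added after methanol, and to which tubes: the FoxP3 and iNOS single stains, the Treg tube and the CD80/iNOS tube.
- Check the bench records. In the analyses of sections 9.1.2 and 13.3, exclude FoxP3- and iNOS-defined values only for draws shown to have been run in the written order.

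The cost is an edit to the laboratory method and a records check. The listed panel needs no extra blood or antibodies; a restored tube would draw on the same 1 ml suspension, so its volume has to be stated. The small downside is the possible loss of Treg and iNOS values from draws found to have been run as written.

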9.2. Correlative Study #2

Evaluate levels of circulating cytokines (HGF, TGF- β 1, TGF- β 2, TGF- β 3) and chemokines (CCL2 for M1 macrophages, and CXCL9, CXCL10, and CXCL11 for T-cells).

9.2.1. Background

Immune cell infiltration into malignant tumors is thought to be an important component of a patient having a response to immune checkpoint inhibitors and radiation, however, mechanisms of T-cell and macrophage trafficking have not been well studied in patients receiving immune checkpoint inhibitors or radiation. Changes in cytokine and chemokine levels specific for T-cells and macrophages may correlate with levels of circulating immune cells and tumor response to therapy.

9.2.2. Rationale for Analysis

As above, biomarkers predictive of response to immune therapy are currently not well developed. Levels of circulating cytokines and chemokines for T-cells and macrophages before and during therapy have the potential to help better determine which patients will benefit from therapy. The data from these correlative studies will be used as part of a univariate and multivariate logistic regression model to assess the association between

response to treatment and several variables related to the radiotherapy, tumor, and patient characteristics

9.2.3. Collection of Specimens

After consenting patients, peripheral blood samples will be collected at baseline before initiation of treatment and at the time of any change in response status as assessed on follow-up imaging studies. All attempts will be made to draw the blood with currently scheduled venipuncture, but it will also be permissible to draw specifically for this study if necessary.

9.2.4. Handling of Specimens

Approximately 10-16 mL of blood will be obtained from the patient in two 10 ml EDTA (purple top) tubes. These tubes of blood will serve as the specimen for both correlative study #1 and #2. In order to facilitate the subsequent analyses all research samples will be collected on Monday-Thursday from 8:00am-3:00pm. Specimens will be put on ice after collection and transported to the Biospecimen Processing Core Laboratory (Room 1826 MBRCC) within 30 minutes of acquisition. All subsamples will be labeled with only the following: patient research ID (obtained from the PI/study coordinator), date/time of collection, type of sample. The labeled sample for correlative study #1 and #2 will then be transported on ice to the laboratory of [name] (HSC 5602) for further processing and analysis.

9.2.5. Analytical Laboratory

The specimens will be processed and analyzed in Health Sciences Center (HSC) laboratory 5602, under the direction of [name]. [name] and his personnel will provide technical support for the isolation of both the serum and cellular component of the samples, and provide overall guidance in experimental design and interpretation of results.

9.2.6. Methods

In our sterile biosafety cabinet in lab 5602 HSC, patient whole blood will be diluted 1:2 with sterile phosphate buffered saline (PBS). The mixture will be layered atop 15 mL Ficoll and centrifuged at 1200 rpm for 20 minutes (no break). After, the serum will be collected from the top layer and aliquoted into 1.5 mL Eppendorf tubes and frozen at -80C until further analysis for cytokines/chemokines by ELISA or Multiplex analysis.

Determination of chemokines in plasma:

An aliquot (100 μ L in duplicate) of patient serum will be thawed from -80C storage and subjected to ELISA analysis specific for human CCL2, CXCL9, CXCL10, and CXCL11 (R&D Systems, DuoSet Kits) as described by the manufacturer. Validity of the assay: We will be using standard “sandwich” ELISA kits sold by R&D Systems, Inc. Each kit is built specifically for the detection of human CCL2, CXCL9, CXCL10, and CXCL11 from cell supernatants, homogenized tissue extract, plasma, and serum. The kit is composed of a specific monoclonal “capture” antibody for the protein of interest. After incubation of the sample and binding, a polyclonal “detection” antibody is incubated with the sample followed by a signaling molecule that allows for detection. A standard curve is generated using recombinant protein for quantitative comparison. These samples will be run in duplicate and averaged to minimize error. This is a well-accepted and highly-published method in the literature.

9.3. Correlative Study #3

Immune-Repertoire next generation sequencing (NGS) analysis.

9.3.1. Background

The clonality and diversity of the T-cell receptor (TCR) CDR3 region may help determine the specific lung cancer antigens and host immune response that was triggered by immune therapy and radiation. We will use next generation sequencing of the circulating T-cells immune-repertoire (i-repertoire) to better understand the evolution of tumor response during the course of treatment.

9.3.2. Rationale for Analysis

Assessing the dynamic changes of the immune-repertoire of a patient under checkpoint anti-PD-1 immunotherapy, with the adjunctive addition of local radiotherapy, would allow us to gain insight into the determinant of immunotherapy response. Such knowledge would have significant diagnostic potential when validated in the future in the arena of cancer immunotherapy.

9.3.3. Collection of Specimens

After consenting patients, peripheral blood samples will be collected at baseline before initiation of treatment and at the time of any change in response status as assessed on follow-up imaging studies. All attempts will be made to draw the blood with currently scheduled venipuncture, but it will also be permissible to draw specifically for this study if necessary.

9.3.5. Analytical Laboratory

The specimens will be processed and analyzed in Health Sciences Center (HSC) laboratory 5602, under the direction of [name]. [name] and his personnel will provide technical support for the isolation of both the plasma and cellular component of the samples, and provide overall guidance in experimental design and interpretation of results.

RNA extraction and purification would be performed as outlined above. Purified RNA is then amplified using iRepertoire's HTBI-M Reagent System (barcodes 01-10) per the manufacturer's instructions using Qiagen's One-step RT-PCR and Multiplex Master kit. The amplified band of interest (~500 bp) is extracted and gel purified using Qiagen's Qiaquick Gel Extraction kit. Ten libraries will be pooled for each Illumina MiSeq Flow Cell using equimolar quantities of each amplified library. The pooled libraries will be subjected to a QC and quantification process including Qubit quantification, bioanalysis, and quantification with Kappa qPCR. The libraries will then be sequenced on an Illumina MiSeq capable of 250 paired-end reads. Bioinformatics analysis is performed in conjunction with MBRCC Bioinformatics and Biostatistics Core ([name]). When samples are sent out for NGS and bioinformatics analysis in vendors or collaborators outside of WVU Cancer Institute, MBRCC, samples or data would be fully deidentified and strict HIPAA regulation compliance will be followed.

10. STUDY PARAMETERS AND CALENDAR

10.1. Study Parameters

10.1.1. Screening Evaluation

All evaluations must be completed \leq 28 days prior to administration of protocol therapy with documentation of the following elements:

- Informed Consent
- Demographics:
 - Patient age & gender
 - Full oncologic history including all prior cancer-directed therapies and their dates of administration.
 - Smoking history (active, past, or nonsmoker; number of pack-years)
 - History of weight loss or oral corticosteroid use in the past 3 months, autoimmune conditions, dialysis, cirrhosis, splenectomy, mental illness, diabetes mellitus, statin use, metformin use, and recurrent infections in the past 6 months (including location, frequency, severity, duration, complications, and infections with unusual organisms).
 - For females, assessment of childbearing potential
 - Baseline Symptoms Assessment and Review of Systems
- History & physical exam
- Height, weight, ECOG performance status, and vital signs (including blood pressure, pulse, respiratory rate, and temperature)
- Concomitant medications assessment
- PD-L1 status of any pre-treatment biopsy specimen
- Laboratory Studies:
 - Non-fasting:
 - Complete Blood Count (CBC) with differential and smear
 - Serum Chemistries: sodium, potassium, chloride, bicarbonate, BUN, creatinine, glucose, calcium, magnesium, phosphorous, albumin
 - Liver Function Tests: alkaline phosphatase, total bilirubin, total protein, SGOT [AST], SGPT [ALT]
 - Thyroid Function Tests (TSH)

- Urinalysis (macroscopic and microscopic) with culture reflex
- Special circumstances:
 - Serum β -HCG for women of childbearing potential
 - Hemoglobin A1c for diabetic patients
- Imaging:
 - Full body PET/CT scan (preferred) or CT chest, abdomen, and pelvis with IV contrast.
 - CT brain or MRI brain (preferred) with IV contrast
- Quality of Life Questionnaires ([Appendix C](#)):
 - The validated Functional Assessment of Cancer Therapy (FACT) instrument will be used to assess physical, social/family, emotional and functional well-being, and additional questions specific for lung cancer patients (FACT-L) and fatigue (FACIT Fatigue Scale). These validated instrument is user friendly (can be completed in less than 10 minutes) and has been used extensively to measure QOL in lung cancer patients.⁴¹⁻⁴²

10.1.2. Treatment Period & Follow-up

All medical care provided on the days of immune checkpoint therapy administration will be at the discretion of the treating medical oncologist according to standard of care. No specific data will be recorded from these visits, but at the subsequent study follow-up visit all prior administrations of immune therapy (date and dose) will be recorded. All treatment data related to the radiotherapy will be recorded on the first and last day of each course, and will include the start and end date of the radiotherapy course, total dose, dose per fraction and number of fractions of radiation received during the course. Data from follow-up studies will be recorded as per the study calendar in section 10.2.

10.2. Study Calendar

Parameters	≤28 days prior to registration	Day 1 of immune therapy	Last day of first course of RT	Follow-up before documented progressive disease, at 3, 6, 9, and 12 months after initial cycle of immune therapy ¹	Follow-up before documented progressive disease, beyond 12 months after initial cycle of immune therapy is timed per standard of care at treating physicians' discretion	Follow-up after progressive disease or switch to alternative systemic therapy ²
Informed Consent	X					
Demographics	X					
History and Physical Exam	X ³			X ¹⁵	X	
Wt/Vitals/ ECOG PS	X			X ¹⁵	X	
Concomitant Med Assessment	X			X ¹⁵		
FACT/FACIT Questionnaire ⁴		X		X ¹⁵		
Serum CBC/diff/platelets ⁵	X			X ²		
Serum chemistries ⁶	X			X ²		
Serum liver function tests ⁷	X			X ²		
Serum TSH	X			X ²		
Urinalysis with reflex culture	X					
Serum β-hCG ⁸	X					
Hemoglobin A1c ⁹	X					
MRI (preferred) or CT brain with IV contrast	X					
FDG-PET/CT (preferred) or CT chest/abdomen/pelvis with IV contrast ¹⁰	X			X ¹⁶	X	
Research blood sample ¹¹		X		X ¹⁷	X ¹⁷	
Immunotherapy Administration Assessment ¹²		X	X	X	X	
Radiation Therapy Administration Assessment ¹³			X	X	X	
Survival assessment ¹⁴						X
AE/SAE Assessment ¹⁹	X	X	X	X	X	
PD-L1 status ²⁰	X					
Rebiopsy (optional)				X ¹⁸	X ¹⁸	X ¹⁸

¹The final formal assessment will be at time of documented disease progression.

²To be performed according to standard of care.

³To be documented by treating radiation oncologist. Vital signs to include blood pressure, pulse, respiratory rate, and temperature

⁴See [Appendix C](#) for questionnaires, which will be administered electronically using REDCap. A research assistant will open the questionnaire weblink (<http://j.mp/2eLzfjE>) on a password protected tablet computer, enter the patient's study ID into the survey instrument, and then the patient will complete the rest of the electronic form and submit it. The research assistant will be available to answer any questions that the patients have, if necessary. Details on REDCap can be found in Section 12.1 below. The initial questionnaire may be done anytime between signing the consent and the first immune therapy treatment. The questionnaires may be completed using paper forms if REDCap is unable to be accessed or based on patient preference.

⁵CBC with differential includes hemoglobin, hematocrit, white blood cell count, absolute neutrophil count, and platelets

⁶Serum chemistries include sodium, potassium, chloride, bicarbonate, BUN, creatinine, glucose, calcium, magnesium, phosphorous, albumin

⁷Serum liver function tests include alkaline phosphatase, total bilirubin, total protein, SGOT [AST], SGPT [ALT]

⁸Only for women of childbearing potential (within 14 days of registration)

⁹Only for patients with diabetes mellitus

¹⁰In patients with contrast allergy a short course of steroids may be given as needed. In patients with poor kidney function in whom contrast is contraindicated a non-contrast imaging study is permissible.

¹¹Please refer to protocol section 9 for details. The initial research blood sample may be drawn anytime between signing the consent and the first immune therapy treatment.

¹²Record all past and current administrations of immune therapy (sections 5.2 and 6.2), including date and dose of each administration.

¹³Record all past and current administrations of radiation therapy (sections 5.1, 5.3, and 6.1), including for each course: the start and end date, total dose, dose per fraction, number of fractions, and location of treated lesion.

¹⁴Survival assessment may be carried out via chart review or phone call only.

¹⁵A window of \pm 14 days around the standard time point every 3 months is allowed as necessary

¹⁶A minimum of one scan every 4 months is required, however, scans may be completed at more frequent intervals as clinically indicated.

¹⁷Performed in coordination with imaging studies, at baseline prior to treatment, and thereafter only for a change in extracranial response on follow-up imaging. The blood will be drawn within 30 days of any imaging study showing a change in extracranial response status.

¹⁸Optional rebiopsy of an accessible non-irradiated tumor may be obtained at the treating physicians' discretion if it is deemed clinically warranted and safe to perform, for diagnostic purpose in order to confirm progression of disease and underlying histopathology. If indicated, it should be carried out within 30 days of the confirmatory imaging study showing disease progression, and prior to initiating any further systemic therapy.

¹⁹AEs and SAEs will be collected on a continuous basis starting with the first cycle of immune therapy. Both AEs and SAEs will be collected up until 30 days after the last dose of immune therapy or until the patient begins a new cancer-directed therapy, or death, whichever comes first.

²⁰PD-L1 status (percentage staining by immunohistochemistry) of any pre-treatment biopsy specimen is not required for eligibility, but if information is available at any time point prior to or after enrolling in the trial, this data will be collected in the EDC.

